9.1 Efficacy Assessments

Study evaluations will take place in accordance with the Schedule of Assessment (Section 2). Baseline assessments should be performed within 28 days prior to first dose utilizing CT or MRI. In addition to chest, abdomen, pelvis, and brain, all known sites of disease should be assessed at baseline. Participants who cannot receive IV contrast for CT at the start of study should be imaged by MRI of abdomen/pelvis with IV contrast and CT of chest without contrast. Subsequent assessments should include chest, abdomen, and pelvis, and all known sites of disease and should use the same imaging method as was used at baseline. Participants initially imaged with CT of chest, abdomen, and pelvis with IV contrast who can no longer receive contrast can be monitored by CT of chest, abdomen, and pelvis without IV contrast. Please refer to additional precautions

regarding IV contrast in [Section 7.7.2.3](#). Participants in all cohorts will be evaluated for tumor response at the following intervals and time points:

- First tumor assessment should be performed at 12 weeks (± 1 week) following first dose. Subsequent tumor assessments should occur every 8 weeks (± 1 week) up to first 13 months, then every 12 weeks until disease progression or treatment discontinuation, whichever is later

For Cohorts 3 and 4: Brain lesion(s) that are < 10 mm or that have been previously irradiated will only be assessed as non-target lesion per RECIST 1.1. Brain lesions that are ≥ 10 mm and that have not been previously irradiated will be assessed as target lesions per RECIST 1.1.

Participants will be permitted to continue treatment beyond PD (RECIST 1.1) under protocol-defined circumstances (See [Section 7.9](#)). Tumor assessments for ongoing study treatment decisions will be completed by the investigator using RECIST (Response Evaluation Criteria in Solid Tumors) 1.1 criteria.

9.1.1 *Imaging Assessment for the Study*

Images will be submitted to the local lab, and read locally by the site Radiologist.

Table 9.1.1-1: Imaging Assessment Schedule (Cohort 1)

Study Day	Event Relative to Dosing	CT/MRI
Screening	Pre-dose	X
Week 12 (± 1 week)	Post-dose	X
Every 8 weeks (± 1 week)	Post-dose	X
Every 12 weeks (± 1 week), after Month 13 of treatment	Post-dose	X

Table 9.1.1-2: Imaging Assessment Schedule (Cohorts 2, 3 and 4)

Study Day	Event Relative to Dosing	CT/MRI
Screening	Pre-dose	X
Week 12 (± 1 week)	Post-dose	X
Every 8 weeks (± 1 week)	Post-dose	X
Every 12 weeks (± 1 week), after Month 13 of treatment	Post-dose	X

[REDACTED]

9.2 Adverse Events

The definitions of an AE or serious adverse event (SAE) can be found in [Appendix 9](#).

AEs will be reported by the participant (or, when appropriate, by a caregiver, surrogate, or the participant's legally authorized representative).

The investigator and any designees are responsible for detecting, documenting, and reporting events that meet the definition of an AE or SAE and remain responsible for following up AEs that are serious, considered related to the study treatment or the study, or that caused the participant to discontinue before completing the study.

Immune-mediated adverse events are AEs consistent with an immune-mediated mechanism or immune-mediated component for which non-inflammatory etiologies (eg, infection or tumor progression) have been ruled out. IMAEs can include events with an alternate etiology which were exacerbated by the induction of autoimmunity. Information supporting the assessment will be collected on the participant's case report form.

Contacts for SAE reporting specified in Appendix 9.

9.2.1 Time Period and Frequency for Collecting AE and SAE Information

The collection of non-serious AE information should begin at initiation of study treatment until the follow-up contact, at the time points specified in the Schedule of Activities (Section 2). Nonserious AE information should also be collected from the start of a placebo lead-in period or other observational period intended to establish a baseline status for the participants.

Sections 5.6.1 and 5.6.2 in the Investigator Brochure (IB) represent the Reference Safety Information to determine expectedness of serious adverse events for expedited reporting. Following the participant's written consent to participate in the study, all SAEs, whether related

or not related to study drug, must be collected, including those thought to be associated with protocol-specified procedures.

All SAEs must be collected that occur during the screening period and within 100 days of discontinuation of dosing. If applicable, SAEs must be collected that relate to any later protocol-specified procedure (e.g., a follow-up skin biopsy).

The investigator must report any SAE that occurs after these time periods and that is believed to be related to study drug or protocol-specified procedure.

- Medical occurrences that begin before the start of study treatment but after obtaining informed consent will be recorded on the appropriate section of the eCRF section.
- All SAEs will be recorded and reported to Sponsor or designee within 24 hours, as indicated in [Appendix 9](#).
- The investigator will submit any updated SAE data to the sponsor within 24 hours of this being available.

Investigators are not obligated to actively seek AEs or SAEs in former study participants. However, if the investigator learns of any SAE, including a death, at any time after a participant has been discharged from the study, and he/she considers the event reasonably related to the study treatment or study participation, the investigator must promptly notify the sponsor.

The method of evaluating, and assessing causality of AEs and SAEs and the procedures for completing and reporting/transmitting SAE reports are provided in [Appendix 9](#).

9.2.1.1 Adverse Events of Special Interest – Immune-mediated AEs

Immune-mediated AEs (IMAEs) are specific events (or groups of PTs describing specific events) that include pneumonitis, diarrhea/colitis, hepatitis, nephritis/renal dysfunction, rash, endocrine (adrenal insufficiency, hypothyroidism/thyroiditis, hyperthyroidism, diabetes mellitus, and hypophysitis), and other specific events, considered as potential immune-mediated events by investigator, that meet the definition summarized below:

- those occurring within 100 days of the last dose
- regardless of causality
- with no clear alternate etiology based on investigator assessment, or with an immune-mediated component
- treated with immune-modulating medication (Of note, adrenal insufficiency, hypothyroidism/thyroiditis, hyperthyroidism, diabetes mellitus, and hypophysitis are considered IMAEs regardless of immune-modulating medication use, since endocrine drug reactions are often managed without immune-modulating medication).

[Table 9.2.1.1-1](#) below provides a summary of the IMAEs category and their respective preferred terms.

Table 9.2.1.1-1: Preferred Terms Included in Analysis of IMAEs to Support Warnings and Precautions

IMAE Category	PTs included under IMAE Category
Pneumonitis	Pneumonitis, interstitial lung disease
Diarrhea/Colitis	Diarrhea, colitis, enterocolitis
Hepatitis	Hepatotoxicity, hepatitis, hepatitis acute, autoimmune hepatitis, AST increased, ALT increased, bilirubin increased, ALP increased
Adrenal insufficiency	Adrenal insufficiency
Hypothyroidism/Thyroiditis	Hypothyroidism, thyroiditis Thyroiditis acute (collapsed with thyroiditis for frequency), Autoimmune thyroiditis (collapsed with thyroiditis for frequency)
Hyperthyroidism	Hyperthyroidism
Hypophysitis	Hypophysitis
Diabetes mellitus	Diabetes mellitus, diabetic ketoacidosis
Nephritis and renal dysfunction	Nephritis, nephritis allergic, tubulointerstitial nephritis, acute renal failure, renal failure, increased creatinine
Rash	Rash, rash maculopapular

9.2.2 Method of Detecting AEs and SAEs

Adverse events can be spontaneously reported or elicited during open-ended questioning, examination, or evaluation of a participant. (In order to prevent reporting bias, participants should not be questioned regarding the specific occurrence of one or more AEs.)

9.2.3 Follow-up of AEs and SAEs

- Nonserious AEs should be followed to resolution or stabilization, or reported as SAEs if they become serious (see [Appendix 9](#)).
- Follow-up is also required for nonserious AEs that cause interruption or discontinuation of study treatment and for those present at the end of study treatment as appropriate.
- All identified nonserious AEs must be recorded and described on the nonserious AE page of the CRF (paper or electronic). Completion of supplemental CRFs may be requested for AEs and/or laboratory abnormalities that are reported/identified during the course of the study.

After the initial AE/SAE report, the investigator is required to proactively follow each participant at subsequent visits/contacts. All SAEs, and non-serious AEs of special interest (as defined in [Section 9.2](#) will be followed until resolution, until the condition stabilizes, until the event is otherwise explained, or until the participant is lost to follow-up (as defined in [Section 8.3](#)).

Further information on follow-up procedures is given in [Appendix 9](#).

9.2.4 Regulatory Reporting Requirements for SAEs

- Prompt notification by the investigator to the Sponsor of SAEs is essential so that legal obligations and ethical responsibilities towards the safety of participants and the safety of a product under clinical investigation are met.
- An investigator who receives an investigator safety report describing SAEs or other specific safety information (e.g., summary or listing of SAEs) from the Sponsor will file it along with the Investigator's Brochure and will notify the IRB/IEC, if appropriate according to local requirements.

Sponsor or designee will be reporting adverse events to regulatory authorities and ethics committees according to local applicable laws including European Directive 2001/20/EC and FDA Code of Federal Regulations 21 CFR Parts 312 and 320. A SUSAR (Suspected, Unexpected Serious Adverse Reaction) is a subset of SAEs and will be reported to the appropriate regulatory authorities and investigators following local and global guidelines and requirements.

All SAEs must be collected that occur during the screening period and within 100 days of the last dose of study treatment. For participants assigned to treatment and never treated with study drug, SAEs should be collected for 30 days from the date of treatment assignment.

9.2.5 Pregnancy

If, following initiation of the study treatment, it is subsequently discovered that a participant is pregnant or may have been pregnant at the time of study exposure, including during at least 5 half-lives after product administration, the investigator must immediately notify the BMS Medical Monitor/designee of this event and complete and forward a Pregnancy Surveillance Form to BMS Designee within 24 hours of awareness of the event and in accordance with SAE reporting procedures described in [Appendix 9](#).

In most cases, the study treatment will be permanently discontinued in an appropriate manner (e.g., dose tapering if necessary for participant safety). Please call the BMS Medical Monitor within 24 hours of awareness of the pregnancy. Protocol-required procedures for study discontinuation and follow-up must be performed on the participant.

Follow-up information regarding the course of the pregnancy, including perinatal and neonatal outcome and, where applicable, offspring information must be reported on the Pregnancy Surveillance Form.

Any pregnancy that occurs in a female partner of a male study participant should be reported to Sponsor or designee. In order for Sponsor or designee to collect any pregnancy surveillance information from the female partner, the female partner must sign an informed consent form for disclosure of this information. Information on this pregnancy will be collected on the Pregnancy Surveillance Form.

9.2.6 Laboratory Test Result Abnormalities

The following laboratory test result abnormalities should be captured on the nonserious AE CRF page or SAE Report Form electronic, as appropriate. Paper forms are only intended as a back-up option when the electronic system is not functioning.

- Any laboratory test result that is clinically significant or meets the definition of an SAE
- Any laboratory test result abnormality that required the participant to have study treatment discontinued or interrupted
- Any laboratory test result abnormality that required the participant to receive specific corrective therapy

It is expected that wherever possible, the clinical rather than laboratory term would be used by the reporting investigator (e.g., anemia versus low hemoglobin value).

9.2.7 Potential Drug Induced Liver Injury (DILI)

Wherever possible, timely confirmation of initial liver-related laboratory abnormalities should occur prior to the reporting of a potential DILI event. All occurrences of potential DILIs, meeting the defined criteria, must be reported as SAEs (see [Section 9.2](#) and [Appendix 9](#) for reporting details).

Potential drug induced liver injury is defined as:

- 1) AT (ALT or AST) elevation > 3 times upper limit of normal (ULN)
AND
- 2) Total bilirubin > 2 times ULN, without initial findings of cholestasis (elevated serum alkaline phosphatase),
AND
- 3) No other immediately apparent possible causes of AT elevation and hyperbilirubinemia, including, but not limited to, viral hepatitis, pre-existing chronic or acute liver disease, or the administration of other drug(s) known to be hepatotoxic.

9.2.8 Other Safety Considerations

Any significant worsening noted during interim or final physical examinations, electrocardiogram, x-ray filming, any other potential safety assessment required or not required by protocol should also be recorded as a nonserious or serious AE, as appropriate, and reported accordingly.

9.3 Overdose

An overdose is defined as the accidental or intentional administration of any dose of a product that is considered both excessive and medically important. All occurrences of overdose must be reported as an SAE (see [Section 9.2](#)).

In the event of an overdose the investigator should:

- 1) Contact the Medical Monitor immediately
- 2) Closely monitor the participant for AEs/SAEs and laboratory abnormalities
- 3) Document the quantity of the excess dose as well as the duration of the overdosing in the CRF.

Decisions regarding dose interruptions or modifications will be made by the investigator in consultation with the Medical Monitor based on the clinical evaluation of the participant.

9.4 Safety

Planned time points for all safety assessments are listed in the Schedule of Activities.

9.4.1 Physical Examinations

Refer to Schedule of Activities.

9.4.2 Vital signs

Refer to Schedule of Activities.

9.4.3 Electrocardiograms

Refer to Schedule of Activities.

9.4.4 Clinical Safety Laboratory Assessments

Investigators must document their review of each laboratory safety report. Please refer to the Schedule of Activities in [Section 2](#) for details related to the required laboratory assessment.

9.4.5 Imaging Safety Assessment

Any incidental findings of potential clinical relevance that are not directly associated with the objectives of the protocol should be evaluated and handled by the Study Investigator as per standard medical/clinical judgment.

10 STATISTICAL CONSIDERATIONS

10.1 Sample Size Determination

The sample size of the study is mainly determined by the feasibility concern. The study plans to enroll 200 participants, 100 in Cohort 1, 50 in Cohort 2, 25 in Cohort 3, and 25 in Cohort 4 (100 in Cohort 1 and 100 in Cohorts 2-4 combined). Enrollment in Cohort 1 for participants with a favorable risk score will be capped at 25% of the total population to be enrolled in that cohort.

In general, the combination of nivolumab and ipilimumab has higher rates in IMAE of high grade (Grade 3-4) than nivolumab monotherapy. Study CA209016 reports that both combination treatment arms have approximately 40-60% high grade IMAEs (34.0% in N3+I1 arm and 63.8% in N1+I3 arm); study CA209012 (for NSCLC) reports approximately 35% high grade IMAEs in both combined therapy arms. Given these reported values, the precision of half width of 95% confidence interval of AE rates is between 9.3% and 9.8% for 100 participants and between 6.6% and 6.9% for 200 participants pooled together. These precisions are deemed as acceptable in evaluating the research hypotheses with respect to study cohorts in terms of AE rates in the range reported by previous studies.

10.2 Populations for Analyses

For purposes of analysis, the following populations are defined:

Population	Description
Enrolled	All enrolled participants: all participants who signed an informed consent form and were registered into the IVRS.
Treated	All treated participants: all participants who received any nivolumab. This is the primary population for safety and efficacy analyses. .
Response Evaluable	All response evaluable participants: all treated participants who have baseline and at least one on-study evaluable tumor measurement.

10.3 Statistical Analyses

Detailed analyses will be specified in the statistical analysis plan separately. In general, unless expressly stated otherwise, all analyses will be performed by Cohort 1, and Cohorts 2-4 combined.

Demographics, baseline disease characteristics and baseline laboratory results will be summarized using descriptive statistics for all treated participants.

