Participants should receive nivolumab at a dose of 6 mg/kg as about a 60-minute IV infusion, and ipilimumab at a dose of 1 mg/kg as about an 30-minute IV infusion on Day 1 Week 1 of each cycle (every 8 weeks), until progression, unacceptable toxicity, withdrawal of consent, the study ends or up to a maximum of 24 month whichever occurs first. Participants should begin study treatment within 5 calendar days of treatment assignment. Beginning on Day 1 of Week 5 of Cycle 1, participants will receive nivolumab 480 mg flat dose, as a 60 minute infusion, and then again every 8 weeks until progression, unacceptable toxicity, withdrawal of consent, the study ends or up to a maximum of 24 month whichever occurs first.

7.1.2 Cohorts 2, 3, and 4

Participants in Cohorts 2, 3, and 4, will receive nivolumab at a dose of 3 mg/kg as a 60 minute infusion, and ipilimumab at a dose of 1 mg/kg as a 30 minute infusion on Day 1 Week 1 and Day 1 Week 4 of each cycle (every 6 weeks) until for up to 4 doses (2 cycles). Participants should begin study treatment within 5 calendar days of treatment assignment. Beginning with Cycle 3 (6 weeks [\pm 3 days] from last combo dose), participants in Cohorts 2, 3 and 4 will receive nivolumab at a dose of 480 mg as a 60 minute infusion every 4 weeks (\pm 3 days) until progression, unacceptable toxicity, withdrawal of consent, the study ends, or up to a maximum of 24 months, whichever occurs first.

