3 OBJECTIVES

3.1 Primary Objective

The primary objectives of this study are:

1. To assess the incidence of high grade (CTCAE v4 Grade 3-4 and Grade 5) IMAEs in participants with advanced or metastatic RCC who are treated with combination therapy of nivolumab 6 mg/kg + ipilimumab 1 mg/kg every 8 weeks alternating with nivolumab 480 mg flat dose every 8 weeks, staggered every 4 weeks in Cohort 1,
2. To assess the incidence of high grade (CTCAE v4 Grade 3-4 and Grade 5) IMAEs in participants with advanced or metastatic RCC who are treated with combination nivolumab

(3 mg/kg) and ipilimumab (1 mg/kg) every 3 weeks for 4 doses, followed by maintenance nivolumab (480 mg every 4 weeks), in the select subgroups of mRCC participants (nccRCC, asymptomatic brains metastasis, or any histology with KPS 50-60% in Cohorts 2, 3, and 4).

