7.1 General Methods

In general, unless expressly stated otherwise, all analyses will be performed by separated Cohort 1, Cohort 2, Cohort 3 and Cohort 4. Except where otherwise stated in this SAP, all analyses and summaries will be performed for all treated subjects. Analyses based on the combination of Cohorts 2-4 are considered not necessary for CSR as Cohort 4 has low KPS and tolerability may not be the same with other groups.

Unless otherwise noted, the bulleted titles in the following subsections describe tabulations of discrete variables, by the frequency and proportion of subjects falling into each category, by cohorts (with total). Percentages given in these tables will be rounded and, therefore, may not always sum to 100%. Continuous variables will be summarized by cohort (with total) using the mean, standard deviation, median, minimum and maximum values.

Time to event distribution (i.e. progression free survival, overall survival and duration of response) will be estimated using Kaplan Meier (KM) techniques. When appropriate, the median along with 95% CI will be provided using Brookmeyer and Crowley methodology (using log-log transformation for constructing the confidence intervals). Rates at fixed timepoints (e.g. PFS 1 at 6 months) will be derived from the Kaplan Meier estimate and corresponding confidence interval will be derived based on Greenwood formula for variance derivation and on log-log transformation applied on the survivor function $S(t)$.

The CA209 Core Safety DPP refers to several analyses that are to be performed on subjects with extended follow-up. For these summaries, AEs occurring from the time of the first dose of study therapy through 100 days after the last dose of study therapy will be summarized. Further general methods information for the safety analyses, including general methods for AEs and laboratory tests can be found in Section 7.1 of the IO core SAP.

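### The SAP drops the protocol's Cohorts 2-4 combined estimate but keeps a total that mixes two regimens, so the stated precision for primary objective 2 does not apply to the cohorts analysed

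*Protocol*

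**What the plan says.** Protocol 10.3 sets the default grouping: "all analyses will be performed by Cohort 1, and Cohorts 2-4 combined". The grouping follows treatment. Cohort 1 receives "nivolumab 6 mg/kg + ipilimumab 1 mg/kg every 8 weeks alternating with nivolumab 480 mg flat dose every 8 weeks" (SAP 3.1). The other three cohorts share a different regimen: "Participants in Cohorts 2, 3, and 4, will receive nivolumab at a dose of 3 mg/kg as a 60 minute infusion" (protocol 7.1.2), with ipilimumab every 3 weeks for up to four doses, then nivolumab maintenance. The two primary objectives divide the same way.

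Protocol 10.1 and SAP 5 plan 100, 50, 25 and 25 participants and count Cohorts 2-4 together as 100. They give precision for only two sizes: 9.3-9.8% for 100 participants, and "between 6.6% and 6.9% for 200 participants pooled together".

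SAP 7.1 changes the grouping: "all analyses will be performed by separated Cohort 1, Cohort 2, Cohort 3 and Cohort 4". It adds: "Analyses based on the combination of Cohorts 2-4 are considered not necessary for CSR as Cohort 4 has low KPS", and says tolerability may differ there. The same section describes discrete tabulations "by the frequency and proportion of subjects falling into each category, by cohorts (with total)" and says: "Continuous variables will be summarized by cohort (with total)".

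SAP 7.6.1.1 summarises the primary endpoint as a number and percentage of all treated subjects. It specifies no Cohorts 2-4 rate and no confidence interval. SAP 4.2 still censors time to response in Cohorts 2-4 using the combined cohort.

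**The concern.** The protocol's group for objective 2 and the precision that supports it are tied together: 100 participants on one regimen. SAP 7.1 removes the group, but SAP 5 keeps the precision statement. A reader of SAP 5 would expect a rate for the 3-weekly regimen known to within about 10 points. The planned tables would give three rates, each less precise than that.

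The reason for dropping the combination also sits awkwardly with what is kept. If Cohort 4's low performance status argues against pooling Cohorts 2-4, it argues against any total that includes Cohort 4. The four-cohort total includes it and adds about 100 participants on another regimen. That total answers neither primary objective, and its value depends on how many participants each regimen happened to enrol.

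**Working it through.** **Inputs.** Planned sizes are 100, 50, 25 and 25 (protocol 10.1, SAP 5). Reference high-grade IMAE rates run from 34.0% to 63.8% (same sections). This range contains 50%, where a binomial interval is widest.

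**Formula.** Wald 95% half-width = 1.96 × √(p(1−p)/n).

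**Step 1: reproduce the stated figures.**
- n=100: 1.96 × √(0.34×0.66/100) = 9.28 points; at p=0.50, 9.80; at p=0.638, 9.42. The plan states 9.3-9.8.
- n=200: 6.57, 6.93 and 6.66 points. The plan states 6.6-6.9.

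The stated figures are correct for those sizes. For objective 2, n=100 exists only if Cohorts 2-4 are combined.

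**Step 2: the groups SAP 7.1 analyses.**
- Cohort 2, n=50: 1.96 × √(0.34×0.66/50) = 13.1 points; at p=0.50, 13.9.
- Cohorts 3 and 4, n=25 each: 1.96 × √(0.34×0.66/25) = 18.6 points; at p=0.50, 19.6.

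These are √(100/50) = 1.4 times and √(100/25) = 2 times the n=100 values. Exact (Clopper-Pearson) intervals tell the same story: 34 of 100 gives 24.8-44.2%, 17 of 50 gives 21.2-48.8%, and 8 of 25 gives 14.9-53.5%.

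**Step 3: what the total contains.** At the planned sizes Cohort 4 is 25/100 = 25% of the dropped group and 25/200 = 12.5% of the total. Its weight is halved, but it is still there, and half of the total is on the other regimen. As an illustration with assumed rates of 34% in one regimen and 50% in the other, the total is (34+50)/2 = 42%, which is neither regimen's rate.

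**Step 4: where the SAP still uses the combined cohort.** SAP 5 uses it for the sample size and SAP 4.2 for time-to-response censoring. The second should do little numerical harm. The maximum response time in the combined cohort is at least as late as that in each member cohort, so under either rule non-responders are censored after the last response in their own cohort, and the Kaplan-Meier estimates at the response times are unchanged. It is a wording inconsistency.

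**The case against.** The strongest reply is that the SAP's choice is open and reasoned. Protocol 10.3 leaves detail to the SAP and applies its grouping only unless something else is expressly stated; SAP 7.1 expressly states something else. Objective 2 names select subgroups, so three cohort rates answer it on a fair reading, and perhaps more informatively than an average over very different performance status. With counts shown per cohort, a reader can add them up. The Cohorts 2-4 pool is itself a 50:25:25 mixture that may shift with enrolment. All of this stands. It means the change is a documented departure from a default, and that objective 2 is not left without results.

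Two further limits apply. The total in the primary IMAE table is inferred from the general convention in SAP 7.1; SAP 7.6.1.1 does not mention one, and table layouts are left to a separate data presentation plan. Also, no interval is planned for the primary rate, so the half-widths describe the precision of the estimates and not printed limits.

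A reader might go further and infer that the pooled interval would exclude both regimens' true rates whenever they differ by about 14 points. The documents do not support this. No such interval is planned, and the arithmetic treats the expected pooled rate as the observed one. With 100 per regimen and a rate of 34% in one, the exact chance that a pooled Wald interval excludes both true rates is about 6% at a 14-point difference and about 28% at 34% versus 50%. Nor can the gap between the 34.0% and 63.8% arms in protocol 10.1 stand in for the difference between this trial's regimens: the higher figure comes from an N1+I3 arm, and both regimens here use ipilimumab 1 mg/kg.

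The reply does not reach the precision statement, which still describes a group the SAP no longer analyses, or the retention of a wider pool after a narrower one was rejected.

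**Conclusion.** The point holds as a mismatch between the analysis groups and the precision that justifies the sample size. Objective 2 will be answered by cohort, with half-widths of about 13.1-13.9 points (n=50) and 18.6-19.6 points (n=25), where the plan states 9.3-9.8. No rate is planned for the 3-weekly regimen as a whole. The 6.6-6.9 figure for 200 pooled belongs to no objective.

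This rests on the planned cohort sizes, on rates within the cited 34.0-63.8% range, and on Wald intervals, which reproduce the plan's own figures. That the total would appear in the IMAE table is a reading of the general methods. It does not follow that objective 2 is unanswered or that the SAP change was an oversight. The matter is worth correcting because the stated precision is not what the SAP's own analysis delivers, and the correction is cheap.

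**What to change.** - **SAP 7.1 and 7.6.1.1:** keep Cohorts 2, 3 and 4 separate, and also report the high-grade IMAE rate for Cohorts 2-4 combined, as in protocol 10.3. If Cohort 4's tolerability is the worry, add Cohorts 2-3 (performance status at least 70%) as a sensitivity.
- **Same sections:** do not report the four-cohort total for the primary endpoint, or label it as mixing two regimens.
- **Protocol 10.1 and SAP 5:** delete the half-width for 200 pooled, and add those for n=50 and n=25.
- **SAP 4.2:** align the time-to-response censoring rule with the groups analysed.

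If the sponsor prefers a purely by-cohort plan, the alternative is to amend protocol 10.3 and the precision text to say so.

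The cost is one extra table column (two with the sensitivity), some wording, and a less favourable stated precision. No new data are needed.
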